### 10.5 Analysis sets

The analysis of data will be based on different analysis sets according to the purpose of analyses. Participant eligibility for each analysis set will be finalised before the database hard lock.

The Safety analysis set will consist of all randomized participants who received at least one dose of the IMP.

The PK analysis set will consist of those participants in the safety set who have sufficient blood samples taken for at least one of the PK variables to be calculated.

In all populations, analyses will be based on the treatment received, regardless of the randomization (any such deviations will be reported). A participant who withdraws prior to the last planned observation in a trial period will be included in the analyses up to the time of discontinuation.

### 10.6 Safety analyses

Participant disposition will be summarised using descriptive statistics.

Individual participant demographics (age, gender and race) and body measurement data (height, weight and BMI) will be listed and summarised descriptively by treatment group and overall. Other baseline characteristics (e.g., medical history, previous medication) will be listed only.

All adverse event data will be listed and summarised by treatment group, by system organ class (SOC) and preferred term (as per Medical Dictionary for Regulatory Activities [MedDRA] coding), severity and relationship. Any SAEs and/ or AEs that led to withdrawal will be summarised and listed.

Vital signs data (see Section 7.1.1) will be listed and summarized, along with changes from baseline, using descriptive statistics (mean, median, standard deviation, minimum, maximum). Out-of-reference-range values will be flagged as high (H) or low (L) and as being clinically relevant or not: the number of participants presenting out-of-range and clinically relevant values will be summarized.

All safety clinical laboratory data will be listed. Laboratory test results will also be compared to laboratory reference ranges and those values outside of the applicable range will be flagged as high (H) or low (L) and as being clinically relevant or not: the number of participants presenting out-of-range and clinically relevant values will be summarized. The quantitative laboratory data, along with changes from baseline

will be summarized using descriptive statistics (mean, median, standard deviation, minimum, maximum). Change from baseline values at each assessment will be calculated as the assessment value minus the baseline value. The qualitative urinalysis data will be listed only.

All ECG data (PR, QRS, QT, QTcB, QTcF and HR) and overall ECG evaluation will be listed. ECG data, along with changes from baseline will be summarized using descriptive statistics (mean, median, standard deviation, minimum, maximum). Furthermore, categorical analysis of QTcF data will be presented as follows:

- Absolute QTcF interval prolongation
  - QTcF interval > 450 ms
  - QTcF interval > 480 ms
  - QTcF interval > 500 ms
- Change from baseline in QTcF interval
  - QTcF interval increases from baseline > 30 ms
  - QTcF interval increases from baseline > 60 ms

Mean value of change from baseline QTcF parameters will be plotted by group and time point. Out-of-reference-range values will be flagged as being clinically relevant or not: the number of participants presenting out-of-range and clinically relevant values will be summarised.

## 10.7 PK Analyses

The PK analyses will be performed by a PK analysis vendor (bioanalytical laboratory). PK parameters and concentrations data will be summarized using descriptive statistics by treatment, using tabular and graphical displays.

Non-compartmental analysis will be used for estimation of pharmacokinetic parameters. The following pharmacokinetic parameters will be calculated for piperaquine:

- $C_{\max}$  Maximal plasma concentration
- $t_{\max}$  Time at which the maximum plasma concentration occurs
- $t_{1/2}$  Terminal elimination half-life
- $AUC_{0-\infty}$  Area under the plasma concentration-time curve from time 0 extrapolated to infinite time
- $AUC_{0-t}$  Area under the plasma concentration curve from time zero up to the last quantifiable concentration
- $AUC_{0-24h}$  Area under the plasma concentration curve from time zero to 24 hours
- $AUC_{0-72h}$  Area under the plasma concentration curve from time zero to 72 hours
- $AUC_{0-168h}$  Area under the plasma concentration curve from time zero to 168 hours
- $\%AUC_{\text{extrap}}$  Percentage of AUC that is due to extrapolation from  $t_{\text{last}}$  to infinity
- $CL/F$  Apparent total plasma clearance
- $Vz/F$  Apparent volume of distribution during the terminal phase
- $\lambda_z$  Terminal rate constant
- $F_{\text{rel}}$  Relative Bioavailability (Note: If the dose is adjusted in Part 2 of the study the  $F_{\text{rel}}$  calculations will be dose adjusted).

The individual plasma concentration data, and the actual time for piperaquine administration and blood sampling will be used in the derivation of the PK parameters. If there is any doubt in the actual time a sample was taken, then the scheduled time will be used. AUC values will be calculated using the linear/log trapezoidal method, applying the linear trapezoidal rule up to  $C_{\max}$  and the log trapezoidal rule for the remainder of the curve. Samples below the lower limit of quantification (LLOQ) prior to the first

quantifiable concentration will be set to zero. Samples with concentrations below limit of quantification (LOQ) after the first quantifiable concentration will be set to 'missing' and omitted from the analysis. Other PK parameters will be calculated according to standard equations. Details of the PK analysis, including the primary and secondary analysis, will be documented in the PK analysis plan.

## **10.8 Primary Analysis**

The relative bioavailability will be assessed using the ratio of the geometric means for the granule dispersible [test] over the hard tablet [reference] in fasted state for  $AUC_{0-72h}$ ,  $AUC_{0-t}$ ,  $AUC_{0-168h}$ ,  $AUC_{0-\infty}$ , and  $C_{max}$ .

## **10.9 Secondary Analyses**

- The relative bioavailability will be assessed using the ratio of the geometric means for the dispersible granules formulation between fed [high-fat meal, low-fat African meal, and milk] over the dispersible granule formulation fasted [reference] for  $AUC_{0-72h}$ ,  $AUC_{0-t}$ ,  $AUC_{0-168h}$ ,  $AUC_{0-\infty}$ , and  $C_{max}$ .
- PK parameters for the hard tablet (fasted) and the dispersible granule formulations (fasted and fed);  $C_{max}$ ,  $AUC_{0-24h}$ ,  $AUC_{0-72h}$ ,  $AUC_{0-t}$ ,  $AUC_{0-168h}$ ,  $AUC_{0-\infty}$ , time to maximum plasma concentration ( $t_{max}$ ), terminal elimination rate constant ( $\lambda_z$ ), terminal elimination half-life ( $t_{1/2}$ ), apparent volume of distribution during the terminal phase ( $Vz/F$ ), apparent total plasma clearance ( $Cl/F$ ), and percentage of AUC that is due to extrapolation from  $t_{last}$  to infinity (% $AUC_{extrap}$ ).
- AE counts and numbers of subjects with AEs will be summarized for each arm by MedDRA system organ class and preferred term. Concomitant medications, subject withdrawal, vital signs, laboratory tests, and ECG parameters will be summarized.

## **10.10 Interim analyses**

No formal interim analysis is planned for this study, other than the safety/PK report that will be performed for the SRC review at the transition from Part 1 to Part 2.

## **10.11 Deviation(s) from the original statistical plan**

As outlined above, the statistical analysis plan will be written and signed off before the database hard lock. Deviations from the original statistical analysis plans will be avoided, and in the unlikely event that they occur, will be reported and justification will be provided in the final report.

## **10.12 Handling of data**

All data will be inspected for potential errors and a summary of missing data will be generated including the percentages of those with non-missing data, drop outs and replacement of participants. Unrecorded values will be treated as missing. The appropriateness of the method(s) for handling missing data may be reassessed at the data review prior to database lock. Further details on the data handling will be included in the site and/or study data management manual.

## 11 DUTIES OF THE INVESTIGATOR

### 11.1 Investigator's confirmation

This study will be conducted in compliance with the protocol, International Conference on Harmonisation Good Clinical Practice E6 (R2) (ICH-GCP), the EU Clinical Trials Directive (2001/20/ECC), IHI-IRB, NatHREC and TMDA.

### 11.2 Safety reporting

#### 11.2.1 Serious adverse event reporting

All SAEs are to be reported immediately (within 24 hours of awareness of the SAE by the Investigator) to the Sponsor in writing. All written reports should be transmitted to the Sponsor by e-mail using the SAE report form. This includes a description of the event, onset date and type, duration, severity, relationship to the IMP, outcome, measures taken and all other relevant clinical and laboratory data. In exceptional circumstances, an SAE (or follow-up information) may be reported by telephone, followed by a completed SAE report form. The initial report is to be followed by submission of additional information (follow-up SAE form) as it becomes available. Additional information related to safety assessment is provided in Section 8.

Expedited reporting to local Regulatory Authorities (TMDA), Independent Ethics Committee (NatHREC) and Institutional Review Board (IHI-IRB) will be done by the Investigator on behalf of the Sponsor in following their reporting requirements. Reporting mechanism for expedited reporting is demonstrated in Figure 1.

## 12 ETHICAL CONSIDERATIONS

The study will be carried out in accordance to the protocol and with principles enunciated in the current version of the Declaration of Helsinki, the guidelines of Good Clinical Practice (GCP) issued by ICH, the local law and regulatory authority's requirements. In agreement with local requirements, the Independent Ethics Committee (IEC) and regulatory authorities will receive regular safety reports and will be informed about study stop/end.

### 12.1 Independent Ethics Committee (IEC)

Prior to enrolment of any participant into this trial, the study protocol and the informed consent form will be reviewed and approved by the National Health Research Ethics Committee (NaTHREC) in Tanzania.

Premature study end or interruption of the study will be reported within 14 days by the Sponsor or by the PI to the IRB and IECs. The regular end of the study and the final clinical study report will be submitted in accordance with the applicable timelines after the end of the study.

### 12.2 Evaluation of the risk-benefit ratio

Potential risks with PQP are mentioned in Section 20.5 . The participants will not profit from any direct benefit of the study drug, but they may profit from a comprehensive health check. If a chronic or underlying disease is identified, participants will be referred accordingly within the national health system.

In addition, there is the potential that the gained knowledge about new drug formulation could help in malaria control efforts. This could lead to societal benefits if a new PQP formulation improves bioavailability and is less sensitive (PK) to the impact of food.

### 12.3 Participant information and consent

Written informed consent of a participant, using the NaTHREC approved consent form, must be obtained before any study procedure is performed. Upon showing interest, NaTHREC -approved language and an appropriate and study-specific Participant Information Sheet(s) (PIS) will be made available to the potential participant and the opportunity to discuss the study will be given.

The participants will be fully informed orally by the delegated study staff about all aspects of the trial, the potential risks and their obligations. The following general principles will be emphasized:

- The participation in the study is entirely voluntary
- The refusal to participate involves no penalty or loss of medical benefits
- The participant may withdraw from the study at any time
- The participant is free to ask questions at any time to allow him or her to understand the purpose of the study and the procedures involved
- The study involves research of an investigational drug
- There is no direct benefit from participating
- The participant's general practitioner may be contacted to corroborate their medical history or seek additional information
- The participant's blood samples taken as part of the study will be stored at the site and samples may be sent outside Tanzania to collaborating laboratories. These samples will be identified only by code numbers.
- The aims of the study and tests to be carried out will be explained
- Reimbursement will be provided for participation as described in the protocol.
- All relevant clinical and laboratory results (serology, lab tests and interpretations of physical exams) will be shared directly with the concerned participants

- Relevant aspects regarding data protection and confidentiality

The participant will be given enough time to make an informed decision about his/her participation in the study. The participant will be asked to read, and consider the statement before signing and dating the Informed Consent Form. The consent form must be signed and dated by the delegated study staff at the same time as the participant signs. A copy of the fully signed form and PIS will be given to the participant and the original will be retained as part of the study records.

#### **12.4 Registration of clinical trial**

The study will be registered at:

- ClinicalTrials.gov
- Tanzania Clinical Trial Register (TzCTR) - imis2.tmda.go.tz/.

#### **12.5 Participant confidentiality**

The Investigator must assure that participants' confidentiality will be maintained and that their identities are protected from unauthorized parties. Participant's identity will not be disclosed to the Sponsor. The Investigator will maintain a Participant Identification List so that the participants can be identified.

Individual participant medical information obtained as a result of this study is considered confidential and non-anonymized disclosure to third parties is prohibited. Participant confidentiality will be further ensured by utilizing participant identification codes to correspond to treatment data in the computer files. No patient identifiable data will be collected in the eEDC tool except for date of birth, as this information is critical for the inclusion of participants and for the statistical analysis of the data. However, data minimization is applied and only month and year of birth are collected for participants.

As part of the informed consent process, the participants will be informed in writing that representatives of the Sponsor (like monitors, auditors, etc.), a Regulatory Authority or Ethics Committee may require direct access to parts of their medical records relevant to the study, including participants' medical history, and that all personal data will be handled strictly confidentially and in accordance with local data protection laws.

Blood samples collected for PK analysis, which cannot be done in Tanzania will be coded and shipped to Switzerland.

If the results of the study are published, it will be done without providing identifying information on the participants.

#### **12.6 Participants requiring particular protection**

Only healthy and literate participants will be asked to participate in this phase I clinical trial. Female participants must understand and be able to follow the contraception requirements detailed in the ICF.

#### **12.7 Insurance**

A clinical trial insurance will be provided by the Sponsor. A copy of the certificate will be filed in the investigator site file and the trial master file.

The Sponsor is insured to indemnify the Investigator against any claim for damages brought by a participant who suffers from a research related injury during the performance of the trial according to the protocol, except for claims that arise from malpractice and/or negligence. This is covered by the clinical trial's host institute (IHI).

In accordance with local regulations, the Sponsor will contract insurance for all study participants.

The Bagamoyo Clinical Trial Unit (BCTU) will be primarily responsible for providing participant's medical care whether it is related or not related to the study for the duration of the trial. If specialist, emergency care or hospitalization is needed, this will be provided at no cost to the participant at the Bagamoyo District Hospital or referral centers in Dar-es-Salaam, Tanzania.

For all unrelated conditions to the study procedures, the participant will be responsible for seeking and funding this care through the normal channels provided by the Ministry of Health and Social Welfare of Tanzania. The obligation to provide medical care for conditions arising during the trial that are not related to study product or study procedure will end with the last study visit of the participant.

### **12.8 Participant reimbursement**

Participants will not be paid for their participation, but all expenses related to trial participation will be covered by the study. This will include meals during their in-patient stay and reimbursement for the transport fare (incurred when coming to BCTU for scheduled or unscheduled visits). In addition, they will be given 25,000 TZS (~USD 11) as compensation for their time at each scheduled visit and meals or snacks during the study related visits at the site.

### **12.9 Protocol amendments**

All protocol modifications must be documented in writing. A protocol amendment can be initiated by either the Sponsor or any Investigator. The Investigator will provide the reasons for the proposed amendment in writing and will discuss with the Sponsor and the PI. Any protocol amendment must be approved and signed by the Sponsor and the PI and must be submitted to the appropriate IEC for information and approval, in accordance with local requirements, and to Regulatory Authorities if required. Approval by IEC (and Regulatory Authority, if applicable) must be received before any changes can be implemented, except for changes necessary to eliminate an immediate hazard to study participants, or when the change involves only logistical or administrative aspects of the study, e.g. change of telephone number(s).

## 13 QUALITY CONTROL AND QUALITY ASSURANCE: DESCRIPTION OF MEASURES

The PI will ensure that all study personnel are appropriately qualified and trained on all important study related aspects, including a protocol-specific training, GCP training, training on data entry and handling, study interventions and assessments and applicable documentation is maintained on site.

### 13.1 Risk management

The risk management log will be set up by the Sponsor. Potential risks to the study, their assessment and management will be documented by the Sponsor in a Risk Management Log. The log will be updated continuously throughout the study duration.

Special attention will be paid to risks associated with participant safety, critical study procedures and critical data.

### 13.2 Risk identification, assessment and mitigation

#### 13.2.1 Study-specific preventive measures

Participants will require adherence to the preventive measure as described or indicated in Sections 13.2.2 and 13.2.3 below.

#### 13.2.2 Birth control and pregnancy testing

Target group for birth control	Contraception required
Female participants of non-childbearing potential (WONCBP): Defined as either postmenopausal (evidence of menopause based on a combination of amenorrhea for at least one year and increased serum follicle-stimulating hormone (FSH) level ( $>30$ IU/L), or surgical sterilisation (evidence of hysterectomy and/or bilateral oophorectomy)	None
Female participants of childbearing potential (WOCBP)	Reliable contraception in accordance with the Tanzania Clinical Trial Guidelines ( https://www.tmda.go.tz/ ), must start one complete menstrual cycle prior to the first day of dosing and continue until 16 weeks after the IMP administration (to cover a full menstrual cycle of 30 days starting after 5 half-lives of last dose of IMP).  Note: Highly effective birth control methods include: combined (estrogen and progestogen containing) oral/intravaginal/transdermal hormonal contraception associated with inhibition of ovulation, progestogen-only oral/injectable/implantable hormonal contraception associated with inhibition of ovulation, intrauterine device, intrauterine hormone-releasing system, bilateral tubal occlusion, vasectomised partner or sexual abstinence.

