Inclusion/Exclusion Criteria	
Inclusion criteria
 
Participants must fulfil all of the following criteria to be eligible for enrolment in this trial:
 

1. Female or Male aged <math>\geq 18</math> years to <math>\leq 55</math> years at the date of signing informed consent.

2. Ability to provide written, personally signed, and dated informed consent to participate in the trial, in accordance with the ICH Good Clinical Practice (GCP) and applicable regulations, before any trial-related procedures.

3. An understanding, ability, and willingness to fully comply with trial procedures and restrictions.

4. Female participants must agree to follow contraceptive requirements as indicated in Section 13.2.2, from at least 30 days prior to first dosage to 16 weeks after last dosage.

5. Agrees not to donate sperm or ova from the time of the first administration of trial medication until twelve weeks after the end of the systemic exposure of the trial drug.

6. Participants must have a body weight of 50 kg or greater and a BMI between 18.0 <math>kg/m^2</math> - 30.0 <math>kg/m^2</math> (inclusive) at screening.

7. Satisfactory medical assessment with no clinically significant or relevant abnormalities as determined by; medical history, physical examination, vital signs, 12-lead electrocardiogram (ECG) and clinical laboratory evaluation that is reasonably likely to interfere with the participant's participation in or ability to complete the trial as assessed by the Investigator.

 
Exclusion criteria
 
Participants will be excluded from enrolment in this trial if they fulfil any of the criteria below:
 

1. Prior screen failure or randomisation in this trial. NOTE: Participants who initially failed due to temporary non-medically significant issues are eligible for re-screening once the cause has resolved.

2. Female participant who is pregnant (from history, examination or confirmed by a positive serum pregnancy test at screening and/or on Day -1) or breastfeeding.

3. Male participants with a female partner(s) who is (are) pregnant or lactating at screening and/or on Day -1 or is (are) expected to be during the trial period.

4. Has a mental incapacity or language barriers precluding adequate understanding, co-operation, or compliance with the trial requirements.

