### 2.1 Introduction

Case management with highly effective antimalarial drugs has contributed to a decrease in malaria morbidity and mortality. However, preventive administration of antimalarial drugs is also recommended for use in selected high-risk populations, irrespective of malaria infection status, both to treat any unrecognized Plasmodium infections and to prevent new ones. These preventive treatments prevent

or cure undetected malarial illness with the goal to achieve therapeutic drug levels in the blood throughout the period of greatest risk (9). WHO strongly recommends with high-certainty evidence the following malaria chemo preventive therapies: SMC, intermittent preventive treatment in infants (IPTi), and intermittent preventive treatment in pregnancy (IPTp)(1).

Since malaria chemoprevention is administered to otherwise healthy infants, children, and pregnant women (who are either parasite-free or have circulating parasites but are asymptomatic), treatments must be highly safe and well tolerated. PQP has not shown any teratogenic liabilities and is therefore expected to be a potential safe option for malaria prevention in pregnant women and women of child-bearing potential (WOCBP) which is a key asset towards malaria eradication.

Sulfadoxine-pyrimethamine (SP) is recommended for IPTp along with the antenatal care visits starting from the second trimester of pregnancy and IPTi along with infant vaccination taking place usually at 10 weeks, 14 weeks and 9 months of age. Sulfadoxine-pyrimethamine plus amodiaquine (SPAQ) is recommended for SMC as a monthly administration during the malaria season for three to four consecutive months to children between three months and five years of age in areas of highly seasonal malaria transmission (1). In this context, SPAQ demonstrated a protective efficacy of >80 % in Burkina Faso (4).

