### **2.1.3 Mechanism of action, clearance and pharmacokinetics**

PQP's mechanism of action is unknown, but it likely mirrors that of chloroquine, a close structural analogue. Chloroquine binds to toxic haem (derived from the patient's haemoglobin) within the malaria parasite, preventing its detoxification via a polymerisation step (10) PQP is a highly lipophilic compound, is highly bound to proteins (>99%) and tends to accumulate in red blood cells. In humans, PQP has a Tmax of approximately five hours after hard tablet administration. PQP is mainly metabolized by CYP3A4 and to a lesser extent by CYP2C9 and CYP2C19. PQP is also a CYP3A4 inhibitor, and a clinical study of Eurartesim® with midazolam showed a modest increase in the exposure of midazolam (<two-fold)(10). The terminal elimination half-life of PQP is around 22 days for adult patients.

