### 2.1.5 Safety profile and potential risks

Although transient asymptomatic alanine aminotransferase/aspartate aminotransferase (ALT/AST) elevations have been described, including in Phase 1 participants, these are generally mild in severity and considered as uncommon. PQP is known to induce QTc prolongation in human participants (11, 12). The following aspects of the PK and adverse event (AE) profiles of PQP, were considered in determining the Inclusion and Exclusion criteria and in designing the tolerability and safety monitoring of this study:

- PQP is known to cause a QTc interval prolongation, and this effect is concentration-related,
- PQP has a terminal elimination half-life of approximately 22 days, however, approximately 1% of the plasmatic Cmax is predicted at 672 hours (i.e. 28 days) after the administration of 1280 mg in healthy adults (13). Therefore, a follow-up of 30 days is considered acceptable to ensure that possible delayed effects on safety laboratory tests are appropriately documented.

As precautionary measures pertaining to QTc effects of PQP, the European Medicines Agency (EMA) has advised that:

- DHA-PQP (Eurartesim®), not be administered with a meal to avoid food-induced increase in PQP Cmax and consequently possible clinically relevant QTc prolongation,
- Baseline and post-dose electrocardiograms (ECGs) be obtained,
- Recent exposure to concomitant drugs known to induce QTc prolongation be avoided (10,14).

Therefore, during this study, healthy participants with risk factors for QTc prolongation will be excluded and enrolled participants will be monitored for QTc effects through ECG recording.

Clinical monitoring will include periodic biochemistry and haematology measurements as well as regular physical examination and AE recording.

Participants will remain in the Unit under medical supervision until 48 hours following the investigational medicinal product (IMP) administration and will be followed up to Day 30 (+/-1 day).

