### **8.8.1 Pregnancy follow-up**

Through the Informed Consent Process all female participants will be instructed to immediately inform the Investigator if they become pregnant during the study or within the following 3 months after the last dosing and that, pregnancy should be followed through delivery or termination of the pregnancy.

A Pregnancy Form will be completed by the Investigator and submitted to the MMV Study Medical Director and Prime Vigilance preferably within 24 hours after the Investigator becomes aware of the pregnancy. The event of pregnancy itself should not be recorded on the Adverse Event Section of the eCRF. The Investigator will provide counselling to the pregnant participant about the risks of the pregnancy and the possible effects on the fetus and thereafter, she will be asked to give written consent to allow for follow up and further collection of data on her pregnancy and the outcome of the child.

Monitoring of the participant should continue until conclusion of the pregnancy. Any SAEs associated with the pregnancy (e.g., an event in the fetus, an event in the mother during or after the pregnancy, or a congenital anomaly or birth defect in the child, spontaneous abortion) will be reported on the Adverse Event Section of the eCRF if the database has not been locked at that time point. In addition, the updated Pregnancy Form will be regularly submitted with latest information on the course and outcome of the pregnancy as becomes available. The investigator should ensure that the new-born undergoes a thorough clinical investigation within the first 4 weeks after birth and that this assessment is thoroughly documented and submitted on a Pregnancy Form to the Sponsor.

Male participants may continue in the trial if pregnancy of their female partner occurs. A Pregnancy Form will be completed and submitted to the MMV Study Medical Director and Prime Vigilance preferably within 24 hours after the Investigator becomes aware of the pregnancy.

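### The 16 weeks of contraception in Protocol 13.2.2 covers 5 half-lives only; its stated basis (5 half-lives plus a 30-day cycle) needs about 20 weeks

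*Protocol*

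**What the plan says.** Protocol 13.2.2 (Birth control and pregnancy testing) sets both a duration and a reason for it. Contraception must last until "16 weeks after the IMP administration (to cover a full menstrual cycle of 30 days starting after 5 half-lives of last dose" of study drug). Inclusion criterion 4, in the synopsis (1.6) and again in 5.2.1, makes agreement to this period a condition of entry: "from at least 30 days prior to first dosage to 16 weeks after last dosage". The criterion does not repeat the reason.

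The half-life appears in four places, always at about 22 days: the synopsis background, Section 2, Section 2.1.3 ("The terminal elimination half-life of PQP is around 22 days for adult patients") and Section 2.1.5 ("PQP has a terminal elimination half-life of approximately 22 days, however, approximately 1% of the plasmatic Cmax is predicted at 672 hours" after a 1280 mg dose in healthy adults). No shorter value is given. Each participant receives one dose, on Day 1 (Section 4), so first and last dose coincide.

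Section 8.8.1 has a separate window. Women are told to inform the investigator "if they become pregnant during the study or within the following 3 months after the last dosing".

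**The concern.** The rule can be checked directly: 5 half-lives, then one 30-day cycle. At a half-life of about 22 days, 5 half-lives alone use up almost all of the 16 weeks, which leaves no room for the cycle. The near match between 16 weeks and 5 half-lives suggests that the cycle was left out of the sum, although the documents do not say how the figure was reached.

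The period protects participants and is part of an eligibility criterion. As written, a woman who complies fully does not get the margin that 13.2.2 says she gets. The trial's estimates and analyses do not depend on it.

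**Working it through.** **Inputs**

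- Stated duration: 16 weeks (13.2.2; criterion 4 in 1.6 and 5.2.1).
- Stated rule: 5 half-lives, then 30 days (13.2.2).
- Half-life: about 22 days (1.6, 2, 2.1.3, 2.1.5).
- Doses: one, on Day 1 (Section 4).

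**Stated figure in days**

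16 × 7 = 112 days.

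**What the rule requires**

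Required days = 5 × half-life + 30.

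- 5 × 22 = 110 days (15.7 weeks).
- 110 + 30 = 140 days (140 / 7 = 20.0 weeks).
- Shortfall: 140 − 112 = 28 days, or 4 weeks.
- Part of the cycle covered: 112 − 110 = 2 of 30 days.

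The stated 16 weeks is therefore not reproduced by its own rule. It is reproduced, to within 2 days, by 5 half-lives without the cycle.

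**Sensitivity to the half-life**

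The 22 days is approximate, and 2.1.3 gives it for adult patients. The other values below are assumptions.

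| Half-life (days) | 5 half-lives (days) | Plus 30 days | Weeks | Shortfall against 112 days |
|---|---|---|---|---|
| 16.4 | 82 | 112 | 16.0 | 0 |
| 20 | 100 | 130 | 18.6 | 18 |
| 22 | 110 | 140 | 20.0 | 28 |
| 22.4 | 112 | 142 | 20.3 | 30 |
| 25 | 125 | 155 | 22.1 | 43 |

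The first and fourth rows are break-even points. Sixteen weeks meets the full rule only up to (112 − 30) / 5 = 16.4 days, and covers 5 half-lives only up to 112 / 5 = 22.4 days.

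**Other readings of the rule**

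- A 28-day cycle: 110 + 28 = 138 days (19.7 weeks), still 26 days short.
- Four half-lives plus 30 days: 88 + 30 = 118 days (16.9 weeks), still 6 days short.

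**Notification window (a separate point, not an arithmetic error)**

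Three months after dosing is about 91 days, and 112 − 91 = 21 days. A pregnancy conceived between about day 91 and day 112 falls inside the required contraception period but after the period in which the woman has been told to report it.

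**The case against.** The sum itself cannot be rebutted. The case on the other side concerns how much it matters and which figure to change.

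- **Exposure is already very low.** Section 2.1.5 predicts about 1% of Cmax at day 28. Simple decay with a 22-day half-life would leave about 41% at that time (0.5 to the power 28/22), so most of the fall from the peak comes early. Five half-lives of simple decay leave about 3%, and the predicted level is below that by day 28. Assuming 22-day decay from 1% at day 28, a 30-day cycle ending at day 112 would start at day 82 with about 0.18% of Cmax and end with about 0.07%. The planned dose here is 320 mg, not 1280 mg, and Section 2.1 states that "PQP has not shown any teratogenic liabilities". All of this stands, and it keeps the severity down. It does not repair the text, because the rule is written in half-lives and 2.1.5 itself repeats the 22 days.
- **The operative instruction is consistent.** All three places say 16 weeks, so no site or participant receives conflicting durations; only the explanation is off. That is correct. Even so, the explanation is what justifies the period, and the period does not deliver it.
- **Nothing shows which figure was intended.** This also stands. Choosing 20 weeks over a corrected explanation is a judgement, and 13.2.2 also refers to national guidelines that are not available here.
- **The 8.8.1 window serves another purpose.** Nothing requires it to match the contraception period. The investigator's duty to submit a pregnancy form on becoming aware has no stated end, and under 8.8 serious events suspected to be drug-related remain reportable. The mismatch is therefore a matter of alignment and adds nothing to the severity.

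**Conclusion.** The concern holds. On the protocol's own half-life of about 22 days, the stated basis needs about 140 days (20 weeks) and the protocol provides 112 days (16 weeks): about 28 days short, with about 2 of the 30 cycle days covered. For assumed half-lives of 20 to 25 days the shortfall is 18 to 43 days. The conclusion would fail only if the half-life were 16.4 days or less, which no part of the documents supports.

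Confidence is high for the inconsistency and lower for the choice of remedy. The point should be fixed because it affects a participant-protection period and an entry criterion. The clinical risk the protocol describes is low, and nothing in the PK endpoints, sample size or statistical analyses changes.

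**What to change.** **Default.** Change 16 weeks to 20 weeks in 13.2.2 and in inclusion criterion 4 (1.6 and 5.2.1), and state the half-life used, for example: *until 20 weeks after dosing (5 half-lives of about 22 days, i.e. 110 days, plus one 30-day cycle)*. This delivers the protection that 13.2.2 already claims.

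**Alternative.** If the sponsor judges 5 half-lives sufficient, keep 16 weeks, replace the explanation with *5 half-lives, about 110 days*, and drop the cycle. If low residual exposure is the real argument, say so there.

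**With either option.** Extend the 3-month window in 8.8.1 to the end of the contraception period (20 or 16 weeks).

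**Cost.** A wording amendment, plus the consent form if it repeats these figures (the consent pages were not available for review). Section 12.9 requires ethics committee approval, and regulatory approval where applicable, before implementation. The default adds up to 4 weeks of contraception and no visits. Version 3.0 is dated 8 November 2023, after the planned first enrolment in July 2023 and shortly before the planned last participant out in December 2023. Women already dosed may therefore need to be contacted, and a longer period goes beyond the 16 weeks they agreed to, so the ethics committee should be asked how to handle it. The alternative adds only the longer notification window.
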